7.1 Demographic and Baseline Characteristics

The following demographic and baseline characteristics will be summarized for each treatment group, for the combination of both ABBV-8E12 dose groups ("ABBV-8E12 Overall") and for the combination of all treatment groups ("Total Subjects") for the safety dataset.

- Gender (male/female)
- Race (white, black, American Indian/Alaska native, Native Hawaiian or other Pacific Islander, Asian, Other, Multi-Race)
- Ethnicity (Hispanic or Latino)
- Age (years)
- Age group (≤ 65 , > 65)
- Weight for all subjects (kg)
- Weight for all male subjects (kg)

- Weight for all female subjects (kg)
- Height (cm)
- Body mass index (BMI, kg/m²)
- Body mass index category (BMI, kg/m²) (≤ 25 , > 25)

Alcohol and tobacco uses will be summarized for each treatment group, ABBV-8E12 Overall and Total Subjects for the safety dataset. For alcohol use, the number and percentage of subjects who are drinkers, ex-drinkers and non-drinkers (defined as those who have never been a drinker) will be presented. For the tobacco use, the number and percentage of users, ex-users and non-users (defined as those who have never been a user) will be presented. A subject reporting multiple use categories for the different types of tobacco (cigarette, pipe, cigar and chewing tobacco) will be counted in the tobacco user category.

The following baseline efficacy variables will be summarized for each treatment group, ABBV-8E12 Overall and Total Subjects for the intent-to-treat dataset.

- PSPRS total and domain scores
- SEADL score
- UPDRS Part II score
- RBANS scale score
- Color trails test (Parts 1 and 2) completion time
- Letter Fluency Test score
- NNIPPS-PPS total and dimension scores
- CGI-S score
- PSP-QoL total and subscale core and Visual Analog Scale (VAS) scores
- EQ-5D index score and VAS score

Categorical variables will be summarized by the number and percentage of subjects in each category. No comparisons of treatment groups will be performed for alcohol and nicotine uses. Continuous variables will be summarized with descriptive statistics

(number of non-missing observations, mean, standard deviation, median, minimum and maximum). No comparisons between treatment groups will be performed.

7.2 Medical History

The conditions/diagnoses recorded in medical/surgery history eCRF will be coded using the most current version of the Medical Dictionary for Regulatory Activities (MedDRA). Data will be summarized and presented using system organ classes (SOCs) and preferred terms (PTs). The SOC will be presented in alphabetical order and the PTs will be presented in alphabetical order within each SOC. The number and percentage of subjects with any condition/diagnosis and condition/diagnosis in a particular SOC and PT will be summarized for each treatment group, ABBV-8E12 Overall and Total Subjects for the safety dataset. Subjects reporting more than one PT within a SOC will be counted only once for that SOC. No comparison among treatment groups will be performed.

The following progressive supranuclear palsy disease history variables will be summarized for each treatment group, ABBV-8E12 Overall and Total Subjects for the safety dataset.

- Age at onset of symptoms of PSP (years)
- Age when first diagnosed as having PSP (years)
- Years since onset of PSP symptoms (Date of Day 1 – Date of onset)
- Years since PSP diagnosis (Date of Day 1 – Date of diagnosis)
- Family history of PSP (None, biological mother, biological father, full sibling, biological child)

Categorical variables will be summarized with the number and percentage of subjects in each category. Continuous variables will be summarized with descriptive statistics (number of non-missing observations, mean, standard deviation, median, minimum and maximum). No comparisons of treatment groups will be performed.

7.3 Previous and Concomitant Medications

Previous medications are defined as all medications with a start date before the first study drug administration date. Concomitant medications are defined as all medications, other than study drug, taken during the treatment period (i.e., from the first day of study drug administration through 45 days after the last day of study drug administration). Previous and concomitant medications will be coded using the World Health Organization (WHO) dictionary and will be summarized by generic name and Anatomical Therapeutic Chemical (ATC) classification system level 3. The number and percentage of subjects who take at least 1 medication and who take at least 1 dose of each specific medication in the following categories will be summarized for each treatment group, ABBV-8E12 Overall.

- Previous medications for PSP (CMCAT = "PROGRESSIVE SUPRANUCLEAR PALSY MEDICATIONS") will be summarized by the following categories:
 - Antipsychotic medication
 - Antidepressants
 - Medications for Parkinsonian symptoms (including levodopa/carbidopa, dopamine agonists, monoamine oxidase inhibitors, COMT inhibitors, and amantadine).
 - Anti-dementia drugs (CMCLAS3 = ANTI-DEMENTIA DRUGS): cholinesterase inhibitors (donepezil, rivastigmine, galantamine) or memantine for cognitive impairment.
 - Selective benzodiazepines and gamma-aminobutyric acid (GABA) agonists (zolpidem, zaleplon, eszopiclone, alprazolam, clonazepam and lorazepam for sleep and anxiety).
 - Other medications
- Other previous medications
- Concomitant medications for PSP (CMCAT = "PROGRESSIVE SUPRANUCLEAR PALSY MEDICATIONS") will be summarized by the same categories as previous medications for PSP.

- Other concomitant medications

No comparisons of treatment groups will be performed.

8.0 Subject Disposition

The number of subjects who are screened will be summarized and screen failures will be summarized in Total Subjects and by each reason for screen failure.

For subjects who are randomized in the study, the number and percentage of subjects in each randomization disposition category (prematurely discontinued and completed) will be summarized for each treatment group, ABBV-8E12 Overall and Total Subjects.

The number and percentage of subjects who prematurely discontinued study drug or prematurely discontinued from the study will be summarized by reason (primary or any reason) for each treatment group, ABBV-8E12 Overall and Total Subjects. The treatment group differences in the percentage of subjects who discontinued for any reason as well as for each specific reason as the primary will be assessed using Fisher's exact test.

In addition, the following additional summaries will be presented for all randomized subjects:

- The number and percentage of subjects who are enrolled at each site.
- The number and percentage of subjects who prematurely discontinued at each site.

9.0 Study Drug Exposure and Compliance

Summaries of study drug exposure and compliance will be prepared for the safety dataset.

Study drug exposure will be summarized for each treatment group, ABBV-8E12 Overall, and Total Subjects. Duration of exposure is calculated as the last study drug administration date minus the first study drug administration date + 30. Total subject

years of exposure is calculated by summing the duration of exposure across all subjects and dividing this sum by 365 (1 year will be considered to be 365 days). The number and percentage of subjects who have taken a total of 1, 2, 3, 4, 5, 6, 7, 8, 9, 10, 11, 12, 13, and 14 doses of study drug will be summarized. No comparisons of treatment groups will be performed for this summary. In addition, duration of exposure will be summarized with descriptive statistics (number of non-missing observations, mean, standard deviation, median, minimum and maximum duration and total subject years).

At each scheduled dosing visit, the investigator will document whether the subject has received the entire infusion and the volume administered will be recorded in the eCRF if the entire dose is not administered. The percentage of the assigned dose administered will be calculated at each visit. The mean of this percentage across infusions for each subject will be obtained. The descriptive statistics (number of non-missing observations, minimum, mean, median, standard deviation, maximum) based on each subject's mean volume percentage of study drug infusion will be summarized for each treatment group, ABBV-8E12 Overall and Total Subjects.

10.0 Efficacy Analysis

10.1 General Considerations

All efficacy analyses will be conducted on the intent-to-treat dataset unless otherwise specified. Data collected more than 45 days after the last dose of the study drug will not be included in efficacy analyses.

10.2 Primary Analysis of Primary Efficacy Endpoint

The primary efficacy endpoint is the change from baseline to Week 52 visit on the PSPRS total score. The primary analysis population will be subjects in the ITT dataset and the primary analysis will be a likelihood-based, mixed-effects model, repeated measures (MMRM) analysis of the change from baseline to each post-baseline assessment up to and including Week 52. The model will include fixed, categorical effects for treatment, site, visit, baseline score-by-visit and treatment-by-visit interactions, with continuous fixed

covariates for baseline score. The primary comparison will be the contrast between each ABBV-8E12 dose group and placebo group at Week 52. Contrasts between each ABBV-8E12 dose group and placebo at Weeks 12, 24, and 36 and overall across the treatment period will be obtained and will be considered as secondary. An unstructured (co)variance structure will be used to model the within-patient errors. If this analysis fails to converge, compound symmetry (co)variance structures will be tested. The same (co)variance structure will also be used for all MMRM analyses for secondary efficacy variables. Satterthwaite's approximation will be used to estimate denominator degrees of freedom.

The following statistics will be presented on the statistical table of MMRM analysis for change from baseline to each visit (Weeks 12, 24, 36, and 52): descriptive statistics (number of non-missing observations, mean, standard deviation, minimum and maximum) for each treatment group. LS mean and standard error within group will be presented for each treatment group. LS mean, standard error, 95% confidence interval and two-sided nominal *P* value of treatment difference comparing each ABBV-8E12 dose group with placebo will also be presented for each post-baseline visit. The LS mean, standard error, 95% confidence interval and two-sided nominal *P* value of treatment difference comparing each ABBV-8E12 dose group with placebo across the treatment period will be included in the output as well.

In addition, a histogram will be generated to describe the proportion of subjects in each PSPRS response category for each treatment group. The 1-point interval response categories are defined based on PSPRS total score change from the baseline to final starting from the minimum to the maximum of the change score (e.g., ...; $-5 < \text{to} \leq -4$; $-4 < \text{to} \leq -3$; $-3 < \text{to} \leq -2$; $-2 < \text{to} \leq -1$; $-1 < \text{to} \leq 0$; $0 < \text{to} \leq 1$; $1 < \text{to} \leq 2$; $2 < \text{to} \leq 3$;).

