4.3 Sample Size

Approximately 330 PSP subjects (110 subjects/group) will be enrolled and randomized into two ABBV-8E12 dose groups and the placebo group with 1:1:1 randomization ratio. This sample size has ~90% power to detect an ABBV-8E12 effect size (vs. placebo) of 0.56 for the high dose and 0.28 effect size for the low dose on the PSPRS total score changes from baseline at Week 52 using the Bonferroni method to control for multiplicity due to multiple comparisons between two doses and placebo at the two-sided 5% significant level. A no data rate of 25% at Week 52 is assumed in this sample size calculation using East version 6.3.1 (Cytel).

In Japan, a total of 24 subjects (8 subjects/arm) randomized will have 80% probability to detect the consistent treatment effect among three regions (Japan, North America including US/Canada, and European countries including Australia assuming 7%, 54%, and 39% of the total 330 PSP subjects are randomized in three regions, respectively). This calculation is based on Method 2¹ and assumes that the significance level for comparison of each ABBV-8E12 dose vs. placebo is two-sided 2.5% and the dropout rate is 25% in all regions.

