10.3.2 Analysis of Exploratory Efficacy Variables

The exploratory efficacy variables include the following:

- Natural History and Neuroprotection in Parkinson Plus Syndromes-Parkinson Plus Scale (NNIPPS-PPS) total score and dimensional scores
- Patient Global Impression of Change (PGI-C) score
- Letter Fluency Test (words per minute) score
- Repeatable Battery for Assessment of Neuropsychological Status (RBANS) total scale score and subtest scores
- Color Trails Test (Parts 1 and 2) completion time
- EuroQuality of Life (EQ-5D-3L) summary index score and VAS score
- Exploratory quantitative MRI measures including diffusion tensor imaging (DTI) derived fractional anisotropy (FA) and diffusivity measures [radial diffusivity (RD), mean diffusivity (MD), and axial diffusivity (AD)]

The MMRM method used for the primary efficacy analysis will be applied to analyze the change from the baseline to each post-baseline assessment up to the last visit of these exploratory variables with the exception of PGI-C for which the dependent variable is the PGI-C score itself. The model will include fixed, categorical effects for treatment, site, visit and treatment-by-visit interaction, with continuous fixed covariate for baseline score and the baseline score-by-visit interaction in the model. There is no baseline score and baseline score-by-visit interaction in the MMRM model for PGI-C analysis. The comparison will be the contrast between each ABBV-8E12 dose group and placebo group at each post-baseline visit.

The following statistics will be presented on the statistical table of MMRM analysis for change from baseline to each post-baseline visit: descriptive statistics (number of non-missing observations, mean, standard deviation, minimum and maximum) for each treatment group. LS mean and standard error within group will be presented for each treatment group. LS mean, standard error, 95% confidence interval and two-sided nominal *P* values of treatment difference comparing each ABBV-8E12 dose group with placebo will also be presented for each post-baseline visit. No multiplicity adjustment will be conducted for multiple comparisons of exploratory efficacy variables.

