10.6 Handling of Multiplicity

Pairwise comparisons between each ABBV-8E12 dose group and the placebo group will be performed with two-sided tests. Hochberg procedure² will be used for the efficacy analysis to handle multiplicity of comparisons between multiple ABBV-8E12 doses and placebo at the pre-specified significance level at the interim analysis ($\alpha = 0.00001$ at each futility interim analysis), which is described in the DMC Charter.

[figure not shown]
For the final analysis, a graphic approach³ will be used to control overall family wise error rate due to multiple comparisons for primary and key secondary efficacy endpoints for multiple ABBV-8E12 doses. The overall α for the final analysis is 0.04998 after accounting for α spending at interim futility analyses. This α will be split equally between two dose groups to test the efficacy endpoints in the primary and key secondary families within each dose level at Week 52. The order of efficacy endpoints to be tested is PSPRS

total score change at Week 52, UPDRS-II score change at Week 52, CGI-C score at Week 52, midbrain atrophy measured by volumetric MRI change from baseline at Week 52, SEADL score change at Week 52 (Table 3). The primary endpoint will be tested first followed by the secondary endpoints and α could be propagated between two doses and two families of hypotheses testing based on the graphic approach (Figure 2). In the graph, the arrows specify the α transfer paths. Once an endpoint is rejected (i.e., deemed significant) at its assigned significance level, its significance level will be transferred to subsequent endpoint(s) following the arrow(s). If more than one arrow originates from an endpoint, the significance level for this endpoint (once rejected) will be split between multiple subsequent endpoints following the arrows. The numbers on the arrows denote the weights for transferring and (possibly) splitting significance levels. Specifically, the weight 1 denotes 100% transfer of significance level. The number underneath of each hypothesis is the original weight for α splitting assigned to the hypothesis. The overall type I error rate for this trial will be controlled at the two-sided 5% level. Nominal P values and multiplicity adjusted P values for all variables listed in Table 3 will be presented in a table.

Table 3. Hypotheses Testing Order in The Graphical Testing Approach

Efficacy Endpoints Family	Ordered Efficacy Endpoints	Hypotheses	

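### Years since symptom onset is derived but left out of the primary MMRM; adding it could bring a small gain in precision that the documents do not let us quantify

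*SAP*

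**What the plan says.** SAP 10.2 specifies the primary model for change in PSPRS total score at Weeks 12, 24, 36 and 52: "The model will include fixed, categorical effects for treatment, site, visit, baseline score-by-visit and treatment-by-visit interactions". Baseline PSPRS is the continuous covariate and the covariance is unstructured, with compound symmetry as the fallback. Protocol 8.1.3.1 and the synopsis give the same fixed effects.

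SAP 7.2 lists "Years since onset of PSP symptoms" among the disease-history variables, calculated from the onset date to Day 1, and only summarises it. The variable is not a randomisation stratum (SAP 5.2), not in the imputation model (SAP 10.5.1) and not a named subgroup (SAP 10.7). Neither document says why it was left out.

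The SAP does use extra baseline covariates elsewhere. The CGI-C model adjusts for baseline CGI-S, and the volumetric MRI models add head size (SAP 10.3.1). For the patient-rated global change score, SAP 10.3.2 says: "There is no baseline score and baseline score-by-visit interaction in the MMRM model for PGI-C analysis". Protocol 8.1.3.2 agrees.

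**The concern.** The endpoint is one year of progression. Two subjects with the same baseline PSPRS, one symptomatic for a short time and one for longer, have had different average rates of decline before entry. If past rate predicts on-study rate, onset time carries information that baseline PSPRS alone does not. A linear model that adjusts for it targets the same treatment effect with a smaller residual variance. It also guards against chance imbalance in disease tempo, and it may make the missing-at-random assumption somewhat more credible if faster progressors leave earlier.

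The variable is based on the PSP history taken at screening (protocol 5.3.1.1), so no new data are needed. What is at stake is precision only.

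PGI-C raises a smaller point of consistency. Baseline CGI-S and PSPRS are rated on Day 1 before randomisation (protocol Table 7), yet the PGI-C model uses neither, while its clinician-rated counterpart uses CGI-S.

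**Working it through.** **Inputs from the documents (SAP 4.3 unless stated).**
- Size: "Approximately 330 PSP subjects (110 subjects/group) will be enrolled and randomized", allocated 1:1:1, with 25% lacking Week 52 data. Evaluable per arm: 110 × 0.75 = 82.5.
- Significance level: "using the Bonferroni method to control for multiplicity due to multiple comparisons between two doses and placebo at the two-sided 5% significant level", so 0.025 two-sided per dose and critical value 2.2414. SAP 10.6 gives 0.04998 overall at the final analysis, or 0.02499 per dose; power is the same to three decimals.
- Standardised effects: 0.56 for the high dose and 0.28 for the low dose.

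**Reproducing the plan's figure.** SAP 4.3 says: "This sample size has ~90% power to detect an ABBV-8E12 effect size (vs. placebo) of 0.56 for the high dose".
- Power = Φ(d × √(82.5/2) − 2.2414).
- High dose: 0.56 × 6.4226 = 3.5967; Φ(1.3553) = 91.2%, which agrees with the stated figure.
- Low dose: 0.28 × 6.4226 = 1.7983; Φ(−0.4431) = 32.9%.
- Inverse check: 2 × (2.2414 + 1.2816)² / 0.56² = 79.2, so 80 per arm, and 80/0.75 = 107, against 110 planned.

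The sample size therefore does not depend on onset time being in the model.

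**Prognostic strength (assumed).** The documents give none. A simple simulation took symptom duration of 0.5 to 5 years, onset-recall error with SD 0.5 to 1.0 year, and a correlation between past and on-study rate of 0.3, 0.5 or 0.7. The partial R² of onset time given baseline PSPRS was 0.4–0.9%, 2–4% and 5–9% respectively. A second illustrative model with other assumed slopes, noise and recall error ranged from 0.2% to 26%; the top value needs perfect recall and a fully persistent rate.

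**Effect on precision.** The SE is multiplied by √(1 − R²). Power = Φ(d × √(82.5/2/(1 − R²)) − 2.2414). Equivalent extra subjects = 330 × (1/(1 − R²) − 1).

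| Partial R² | SE reduction | High-dose power | Low-dose power | Equivalent extra subjects |
|---|---|---|---|---|
| 0 | 0 | 91.2% | 32.9% | 0 |
| 0.4% | 0.2% | 91.3% | 33.0% | 1 |
| 0.9% | 0.5% | 91.5% | 33.2% | 3 |
| 2% | 1.0% | 91.8% | 33.5% | 7 |
| 5% | 2.5% | 92.6% | 34.6% | 17 |
| 9% | 4.6% | 93.7% | 36.1% | 33 |

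**Validity without the covariate.** A two-arm analysis-of-covariance simulation (82 per arm, 8,000 runs per setting, omitted covariate with R² of 0, 5% or 20%) gave mean estimates of 0.559 to 0.560 for a true 0.56. Type I error was 0.023 to 0.028 against 0.025, within about two Monte Carlo standard errors (0.0017 each).

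**Cost of a useless covariate.** With a coefficient per visit, the Week 52 contrast bears roughly one of the four. The variance inflation is about 1/247.5 = 0.4%, where 247.5 = 3 × 82.5. Charging all four terms to Week 52, with 34 other parameters (30 pooled sites assumed), gives a cautious ceiling of 4/213.5 = 1.9%.

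**Missing onset dates (assumed rates).** If subjects without a date are dropped, high-dose power at R² = 2% is 90.3% with 5% missing and 88.6% with 10% missing, both below 91.2%. If missing values are replaced by the overall mean, R² shrinks to about 0.02 × 0.90 = 1.8% with 10% missing, and power is 91.7%.

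**The case against.** The strongest reply is that nothing in the plan is wrong. The contrast is randomised and already adjusts for site and for baseline PSPRS by visit, and the stated power is reached without onset time. That stands.

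A reader might infer that the model cannot distinguish fast from slow progressors. The documents do not support this: PSPRS is modelled at four visits with unstructured covariance, so observed trajectories inform the fit, and a randomised comparison does not need to separate the two kinds of subject. Those observed scores also do much of the work for missing data. They do not, however, reduce the Week 52 residual variance among completers; a prognostic baseline covariate does.

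A reader might also infer that the precision is free. It is not. Onset is recalled, and inclusion criterion 4 requires only that symptoms began less than 5 years ago, under a broad definition of a symptom; the same limit narrows the covariate's range. Degrees of freedom are spent, a careless missing-date rule would lose more than is gained, and the protocol itself fixes the model.

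Extending the term to the secondary models in SAP 10.3.1 is tempting too. Those models carry other baselines, and no gain has been shown for them.

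PGI-C measures change, so it has no baseline of its own, and it is exploratory. That explains the SAP sentence but does not prevent adjustment for baseline severity, as the CGI-C model shows.

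**Conclusion.** This is an optional efficiency improvement, not an error. The primary analysis is unbiased and holds its type I error as planned. Over the assumed partial R² of 0.4% to 9%, the high dose gains about 0.1 to 2.5 percentage points of power and the low dose about 0.1 to 3.2. The low dose stays far below 90% either way.

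The result rests on that assumed range, on 25% missing at Week 52, and on treating the MMRM contrast as a two-sample comparison of 82.5 per arm. At the bottom of the range, the 0.4% of variance explained is about equal to the variance inflation from the extra term, so the net gain may be nil. The PGI-C change is justified by consistency with the CGI-C model; its size was not calculated.

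**What to change.** - **SAP 10.2.** Before unblinding, add years since onset of PSP symptoms as a continuous covariate with its visit interaction to the primary MMRM.
- **Missing dates.** Complete a partly known onset date from the known year or month. Use the overall mean, regardless of arm, only when the date is wholly missing. Drop no subject.
- **Consistency.** Record the change against protocol 8.1.3.1 and the synopsis. State whether the futility-interim MMRM in SAP 4.4 uses the same model. If it does, make the change before the first futility analysis and recheck the effect-size thresholds. The multiple-imputation analyses in SAP 10.5.1 reuse the primary model, so their imputation model should carry the covariate as well.
- **SAP 10.3.2.** Add baseline CGI-S, as in the CGI-C model, or baseline PSPRS to the PGI-C MMRM, and record this against protocol 8.1.3.2.
- **Leave the SAP 10.3.1 models as they are.**

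The cost is up to four model degrees of freedom (about 0.4% Week 52 variance inflation if onset time is not prognostic), reliance on a recalled date, and a documented departure from the model stated in the protocol. No new data are needed.
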